#### **4.2 Exclusion Criteria**

1. Subjects with any evidence of active malignancy or immunodeficiency disease within the last 30 days. Subjects who have completed therapy and are considered unlikely to relapse or who have had surgery and do not have any evidence of disease, are eligible for the study.
2. Subject using topical steroids on or near the face or immunomodifying drugs, e.g. systemic (oral, intravenous) steroids within the last 30 days; use of inhaled steroids does not exclude a subject from the study.
3. Subject using a nonsteroidal anti-inflammatory drug (NSAID), except for low doses of aspirin ( $\leq 325$  mg/day) used for cardiovascular purposes, or any other analgesic, within 12 hours of calling clinic to report visible signs of a herpetic lesion.
4. Subject has used an investigational drug and/or device within the last 30 days.
5. Subjects who have used any anti-viral drug, or any other systemic or topical medications, including home remedies, intended to treat cold sores (e.g. lysine, topical tea tree oil, topical honey) within the last 30 days.
6. Subject has had a vaccine for herpes simplex virus type 1 (typically oral herpes) or 2 (typically genital herpes).
7. Subject is more than 75 years of age.
8. Subject is pregnant, as checked by subject questioning prior to dosing.
9. Subject has abnormal skin conditions (e.g. acne, eczema, psoriasis, albinism, or chronic vesiculobullous disorders) that occur in the area of the cold sore lesion, or has significant facial hair in the area of the cold sore, that might affect the normal course of the cold sore or might impair accurate evaluation of the cold sore lesion.
10. Subject is currently enrolled in another clinical trial involving a drug and/or device.
11. Subject requires chronic use of analgesics or NSAIDs, except for low doses of aspirin ( $\leq 325$  mg/day) used for cardiovascular purposes. If a subject is unlikely to get through the treatment phase of the protocol without requiring the use of analgesia for a chronic condition, e.g. back pain, recurrent daily headaches, the subject should be excluded.
12. Subject has a recent history of renal dysfunction or serious hepatic disease. Renal dysfunction encompasses both acute and chronic renal failure, the former resulting from the sudden loss of the ability of the kidneys to excrete wastes,

concentrate urine, and conserve electrolytes and the latter resulting from the gradual and progressive loss of these capabilities.

Examples of serious hepatic disease would include alcoholic liver disease, chronic hepatitis, autoimmune hepatitis and a variety of inherited diseases. The underlying cause of a documented recent mild increase in liver enzymes should be considered when deciding whether or not to exclude such a subject.

13. Subject has a history of alcoholism or drug abuse within the preceding 12 months. A subject with a history of a pathological pattern of alcohol use that causes a serious impairment of social or occupational functioning should be excluded. Such subjects may exhibit symptoms of tolerance and withdrawal along with other behavioral symptoms.
14. Subject is institutionalized.
15. Any history which, in the Investigator's judgment, makes the subject ineligible or places the subject at undue risk.
16. Subject is unwilling to comply with the restrictions outlined in Section 5.4 below.

#### **4.3 Restrictions During the Treatment Phase**

1. The subject is not to use any oral or topical prescription or over-the-counter medications to treat the current herpes labialis lesion, or apply any cosmetics, lip balms, ointments, moisturizers or home remedies to the affected area.
2. The subject is not to use any pain medication or NSAID agent, except low doses of aspirin ( $\leq 325$  mg/day) used for cardiovascular purposes, during the Treatment Phase of the study.
3. The subject is not to mechanically disrupt the lesion (i.e. scrubbing, lancing, shaving the area, rubbing with alcohol, etc.).
4. Merlin contains an alpha hydroxyl acid that may increase the skin's sensitivity to the sun and particularly the possibility of sunburn. Subjects should therefore limit sun exposure while using Merlin, and for one week afterwards.

A subject who does not meet one or more of the Inclusion Criteria or certain Exclusion Criteria may still be eligible for continuing in the study. Those subjects would be instructed that they cannot be entered into the Treatment Phase of the study at that time, but must wait until their next outbreak at which time they can call in again to see if they qualify to begin the study treatment.

## 5 Summary of Events

EVENT	Screening 	(Day 0) Treatment Day 	Visit Day 1	Visit Day 2	Visit Day 3 	Visit Day 4	Visit Day 5	Visit Day 6	Visit Day 7	Visit Day 8	Visit Day 9	Visit Day 10	Visit Day 11	Visit Day 12	Visit Day 13	Visit Day 14	F/U 
Clinic visit 	X		X	X	X	X	X	X	X	X	X	X	X	X	X	X	
Informed consent	X																
Enrollment	X																
eligibility criteria																	
Treatment Phase		X 															
eligibility criteria																	
Medical history;	X																
Physical Exam and																	
Vitals																	
Pregnancy test	X	(see footnote 6)															
Treatment		X 	X 	X 	X 	(X) 	(X) 	(X) 									
Subject Diary 		X	X	X	X	X	X	X	X	X	X	X	X	X	X	X	
Diary Review 			X	X	X	X	X	X	X	X	X	X	X	X	X	X	
Clinician lesion		X 	X	X	X	X	X	X	X	X	X	X	X	X	X	X	
assessment 																	
Adverse events 		X 	X	X	X	X	X	X	X	X	X	X	X	X	X	X	
Con meds 	X	X	X	X	X	X	X	X	X	X	X	X	X	X	X	X	

 To be conducted prior to dosing. At this time, subject is instructed on how to apply Merlin and given study materials to take home. If the subject comes into the clinic for screening with an already existing lesion that meets the study criteria, then the subject could begin treatment immediately. In that instance the Screening and Treatment Day would coincide with the Visit Day 1 clinic visit.

 All subjects will be followed daily until Stage 7, reporting daily for a minimum of 3 consecutive days, with the last clinic visit at the time of complete healing or at 14 days, whichever is earlier.

 Treatment Phase eligibility criteria are checked via telephone prior to dosing.

 To be performed by subject. Merlin administrations will begin on Treatment Day. Most typically, it is expected that subjects will treat outside of the clinic on Treatment Day, and come in within 24 hours, (on Visit Day 1), for their first lesion evaluation. If, however, a subject can come in to the clinic for a lesion evaluation the same day as their treatment starts, then Treatment Day and Visit Day 1 will coincide. Treatments will continue through at least Visit Days 1, 2, and 3. If Treatment Day and Visit Day 1 are separate days, then treatment on Visit Day 4 will be administered only if the subject was unable to complete all three (3) sets of treatments on Treatment Day. If Treatment Day and Visit Day 1 coincide, then treatment on Visit Day 5 will be administered only if the subject was unable to complete all three (3) sets of treatments on Treatment Day (Visit Day 1). In either instance a total of twelve (12) treatments (36 applications) over 96 hours from the time of the first treatment is the maximum duration of treatments.

 The first lesion scores, up until first visible signs of a herpetic lesion, are determined by the subject prior to the first treatment. All other lesion scores are determined in the clinic by the Investigator or the Investigator's trained designee.

 For women with child-bearing potential. On Treatment Day "Pregnancy Status" will be determined by asking the subject if she is pregnant or if she has changed her contraceptive practice such that there might be a significantly increased likelihood that she could have become pregnant.

 Treatment Day is the first day a subject reports visible signs of a herpetic lesion, as confirmed by telephone, and is instructed to begin treatment. If the subject can visit the clinic that same day, Treatment Day will coincide with Visit Day 1.

 Minimum duration of study for all subjects, i.e., three (3) consecutive days of clinic visits for lesion, adverse event and concomitant medication assessment.

 Treatment Day Adverse Events will be reported to clinic at the first clinic visit on Visit Day 1.

 Subjects who discontinue prior to Visit Day 3 but have administered any treatment should be followed for safety until at least Visit Day 3.

 The follow-up (F/U) study visit for safety is to be conducted by telephone 2 weeks, or up to 3 weeks, if there are scheduling issues, after the subject completes the Treatment Phase of the study

## 6 Study Endpoints

### 6.1 Efficacy Endpoints

#### 6.1.1 Primary Efficacy Endpoint

The primary efficacy endpoint is the clinician assessed duration of the classical herpetic lesions.

#### 6.1.2 Secondary Efficacy Endpoints

The secondary efficacy endpoints include:

- clinician assessed
  - duration of the herpetic episode (classical and non-classical)
  - duration until complete healing of the herpetic episode (classical and non-classical)
  - prevention of progression to a classical lesion
  - maximum lesion area of the classical lesions
  - cumulative lesion area of the classical lesions
  - cumulative lesion area of all lesions
  - duration of classical herpetic lesion hard scab

#### 6.1.3 Other Efficacy Endpoints

Based on patient diary entries, the other efficacy endpoints include:

- subject assessed:
  - duration of the classical herpetic lesion
  - duration of the herpetic episode (classical and non-classical)
  - duration of complete healing of the herpetic episode (classical and non-classical)
  - prevention of progression to a classical lesion
  - duration of classical herpetic lesion hard scab
  - severity of lesion pain
  - duration of lesion pain

#### 6.1.4 Efficacy Endpoint Definitions

Definitions of the efficacy endpoints are detailed below.

**Duration of the classical herpetic lesion:** Duration is based on staging of the lesion.

Staging is graded as follows: 0=prodromal, 1=erythema, 2=papula/edema, 3=vesicle/pustule, 4=ulcer/soft crust, 5=hard crust, 6=residual swelling/dry flaking, 7=normal skin. The duration of a classical lesion is defined as the time, in hours, from the beginning of treatment to the onset of Stage 6, or, if Stage 6 is never observed, Stage 7. A classical lesion is defined as one that progresses through any of stages 3, 4 or 5.

**Duration of the herpetic episode (classical and non-classical):** For a classical lesion, the duration of the herpetic episode is defined as the time, in hours, from the beginning of treatment until the loss of hard crust (stage 6; residual erythema can be present after loss of

hard crust). For non-classical (aborted) lesions, duration is defined as the time, in hours, from the beginning of treatment until complete resolution of all local signs and symptoms (stage 7).

**Duration until complete healing of the herpetic episode (classical and non-classical):** Duration until complete healing of the herpetic episode is defined as the time, in hours, from the beginning of treatment to the onset of Stage 7, for both classical and non-classical lesions. All subjects will visit the clinic daily, for a minimum of 3 days and a maximum of 14 days, until the lesion reaches Stage 7 with no signs or symptoms of a herpetic lesion.

**Prevention of progression to a classical lesion:** Prevention of progression to classical lesions will be defined as yes for subjects who experience a classical herpetic lesion (i.e., one that passes through any of Stages 3, 4 or 5 (vesicle/pustule, ulcer/soft crust, or hard crust)) and as no for subjects with only aborted, non-classical lesions.

**Maximum lesion area of the classical lesions:** Maximum lesion area of the classical lesions is defined as the maximum lesion area (length x width) for classical lesions during the vesicular, ulcerative, and hard crust stages.

**Cumulative lesion area of the classical lesions:** Cumulative lesion area of the classical lesions is defined as the cumulative lesion area, for which classical lesion areas, day by day, will be added.

**Cumulative lesion area of all lesions:** Cumulative lesion area of all lesions is defined as the cumulative lesion area of both classical and non-classical recurrences.

**Duration of classical herpetic lesion hard scab:** Duration of classical herpetic lesion hard scab will be defined as the assessed duration of the hard crust, stage 5, for the classical lesions. This duration will represent the onset of stage 5 until the time of classical lesion healing at stage 6 or 7, whichever occurs earlier. For lesions that bypass stage 5, duration of hard scab phase will be calculated as time between the two adjacent assessments either side of stage 5.

**Severity of lesion pain:** Pain will be evaluated based on the subject's diary, where the subject will record, just prior to each treatment and three times daily once treatment is complete, the level of pain caused by the defined lesion. The rating scale for pain assessment has four levels for severity: none (1), mild (2), moderate (3), and severe (4).

**Duration of lesion pain:** Duration of pain will be measured in hours from the time of the first occurrence of a pain level of mild, moderate, or severe until a consistent score of a pain level of none has been achieved over at least 2 consecutive pain assessments, or until the lesion is completely healed, whichever occurs first. Subjects who do not reach the no-pain level within 14 days will be considered censored immediately following their last pain assessment. Subjects who never reach a pain level of mild, moderate, or severe will be assigned a duration of pain value of 0 hours.

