
Statistical Methods: Generally, statistical hypothesis tests will be two-tailed, and statistical significance will be declared when the p-value is less than 0.05. Continuous variables will be summarized using descriptive statistics, specifically the mean, median, standard deviation, minimum and maximum. Categorical variables will be summarized by frequencies and percentages.
 
All subjects who received (at least some) treatment, whether they were formally entered into the Treatment Phase of the study or applied the test material without formal authorization, will be included in the Safety Population. The safety analysis will be performed on the Safety Population.
 
All subjects who have been entered into the Treatment Phase of the study will be included in the Modified Intent to Treat (MITT) population. The MITT population will be used as the primary analysis population. All subjects who have been entered into the Treatment Phase of the study and have been followed successfully until their lesion healed, or until 14 days, whichever is earlier, will be included in the Efficacy Evaluable population. The efficacy analysis will be performed on both the MITT and the Efficacy Evaluable populations.
 
No imputation of missing data will be performed for the efficacy analyses for the Efficacy Evaluable population.
 
The duration of the classical herpetic lesion (both clinician and patient assessed) will be analyzed using the Hodges-Lehmann method as the primary efficacy analysis method for estimating the median difference between the two arms. Duration of the herpetic episode (both clinician and patient assessed), duration of complete healing of the herpetic episode (both clinician and patient assessed), duration of the herpetic lesion (both clinician and patient assessed), duration of the herpetic lesion hard scab (both clinician and patient assessed), and duration of pain will be analyzed in the same manner as the duration of the classical lesion.
 
The proportions of subjects in each treatment group who do not display classical lesions (prevention of progression to classical lesions) will be compared using Fisher's Exact Test.
 
For pain, the maximum severity will be analyzed using the Cochran-Mantel-Haenszel Test to test for differences between treatment groups.
		

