#### **10.7.4 Prevention of Progression to Classical Lesions (clinician and patient assessed)**

A classical herpetic lesion is defined as one that passes through any of Stages 3, 4 or 5 (vesicle/pustule, ulcer/soft crust, or hard crust). Prevention of progression to classical lesions will be analyzed by comparing the proportions of subjects in each treatment group who do not display classical lesions. (These are considered aborted lesions.)

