### **7.13.2 Prevention of Progression**

For all endpoints on the occurrence of prevention of progression, counts and percentages will be summarized, and chi-square tests, or Fisher's exact test will be used to compare groups, as appropriate. Fisher's exact tests will be used if any of the expected cell counts in the Rx C crosstabulations are less than 5.

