## **9 Changes from the Protocol**

No changes in the analyses described in the original protocol or subsequent amendments are planned. If changes are made prior to unblinding, this document may be amended and such changes will be described. Changes made after unblinding will be noted in the clinical study report.

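### The SAP codes prevention of progression backwards (yes = the subject had a classical lesion), which reverses the reported direction of a secondary endpoint

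*SAP*

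**What the plan says.** SAP 6.1.4 contains the SAP's only working definition of this variable. It reads "Prevention of progression to classical lesions will be defined as yes for subjects who experience a classical herpetic lesion", identifies a classical lesion by passage through any of Stages 3, 4 or 5, and then continues "and as no for subjects with only aborted, non-classical lesions".

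Protocol 10.7.4 uses the same stages to define a classical lesion but analyses prevention by "comparing the proportions of subjects in each treatment group who do not display classical lesions", and it calls those lesions aborted. The Statistical Methods part of the protocol synopsis agrees: the proportion compared is that of subjects without a classical lesion.

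SAP 6.1.2 lists the clinician-assessed "prevention of progression to a classical lesion" as a secondary endpoint, and SAP 6.1.3 lists the subject-assessed version among the other endpoints. For both, SAP 7.13.2 says "counts and percentages will be summarized, and chi-square tests" or Fisher's exact test will follow. SAP Section 9 states: "No changes in the analyses described in the original protocol or subsequent amendments are planned".

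**The concern.** The coding contradicts the endpoint's own name and the protocol. Since Section 9 announces no change, it cannot be read as a deliberate redefinition.

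A programmer works from SAP 6.1.4. Followed literally, it mislabels the counts and percentages in both planned tables (MITT and EE), for the clinician and the subject versions, overall and separately for subjects treated at Stage 1 and Stage 2. A Merlin benefit would read as harm, and a harm as benefit. The direction matters to the product's case: the protocol's Introduction contrasts existing treatments on exactly this outcome, the share of outbreaks that become classical lesions.

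**Working it through.** The point concerns a definition, and the plan gives no figure of its own to reproduce. The check has two parts.

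**1. The definitions side by side**

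| Subject's lesion | Protocol 10.7.4 and synopsis | SAP 6.1.4 as written |
|---|---|---|
| Any assessment at Stage 3, 4 or 5 (classical) | not prevented | yes (prevented) |
| Aborted, non-classical only | prevented | no (not prevented) |

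Every classified subject falls in the opposite category. Nothing elsewhere in the SAP corrects this: 2.1, 6.1.2 and 6.1.3 only name the endpoint, and 7.13.2 and 7.13.5 give only the summaries and tests.

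**2. The effect on the results**

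Let p be the proportion without a classical lesion. The SAP coding reports 1 − p in each arm, so:

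- Difference, Merlin minus placebo: (1 − p_M) − (1 − p_P) = −(p_M − p_P). The sign reverses.
- Odds ratio: it becomes its reciprocal.
- Chi-square: N(ad − bc)² divided by the product of the four margins. Swapping the columns turns ad − bc into bc − ad, and the square is the same. Fisher's two-sided p-value is also unchanged by relabelling the columns.

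Inputs for an illustration:

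- 75 treated subjects per arm (the minimum in SAP 2.2).
- Placebo aborted 19/75 = 25.3%, close to the 25% given in SAP Section 3 for treatment started at Stage 1. Applying that figure to the placebo arm is an assumption.
- Merlin aborted 26, 30 or 34 of 75. These are assumptions; the documents give no Merlin rate.

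| Merlin aborted | Protocol coding: Merlin vs placebo | Difference | Odds ratio | SAP coding: Merlin vs placebo | Difference | Odds ratio | Chi-square p (both) | Fisher p (both) |
|---|---|---|---|---|---|---|---|---|
| 26/75 | 34.7% vs 25.3% | +9.3 | 1.56 | 65.3% vs 74.7% | −9.3 | 0.64 | 0.212 | 0.285 |
| 30/75 | 40.0% vs 25.3% | +14.7 | 1.96 | 60.0% vs 74.7% | −14.7 | 0.51 | 0.055 | 0.081 |
| 34/75 | 45.3% vs 25.3% | +20.0 | 2.44 | 54.7% vs 74.7% | −20.0 | 0.41 | 0.010 | 0.016 |

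First row worked through: odds ratio = (26 × 56)/(49 × 19) = 1456/931 = 1.56, and its reciprocal is 0.64. Chi-square (uncorrected) = 150 × (1456 − 931)² / (75 × 75 × 45 × 105) = 1.56, giving p = 0.212 under either coding. In the third row a significant benefit would be tabulated as a significant harm.

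**The case against.** Nobody could defend the sentence itself; the case on the other side concerns its consequences.

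- **The reversed table is not certain.** The endpoint's name, the protocol and SAP Section 9 all point the right way, and a programmer may notice. That is possible, but it would mean departing from the SAP's explicit definition. The plan as written yields the reversed result.
- **Other output could expose it.** About 75% prevention on placebo would sit oddly beside the 25% aborted rate in the sample-size section. Protocol 10.7.1 also excludes aborted lesions from the primary analysis, so the number analysed there would roughly match the count coded yes. This is fair, but neither comparison is a planned check.
- **The damage is limited.** The primary endpoint identifies classical lesions separately and correctly, the p-values do not change, and the right result can be recovered from the recorded stages. All of this stands. It bounds the harm but leaves the definition wrong.
- **A Stage 7 condition in the corrected wording goes beyond Protocol 10.7.4.** That section has no such condition. It comes from Protocol 7.3.1, which defines aborted lesions as never passing through Stages 3, 4 or 5 before healing at Stage 7. A subject who leaves, or reaches Day 14, with neither a Stage 3–5 assessment nor Stage 7 is then in neither category. That gap already exists in the SAP, whose no category is confined to aborted lesions, and it is a separate question.

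**Conclusion.** The concern holds. The definition in SAP 6.1.4 is the reverse of the protocol's and must be corrected. Followed as written, it reverses the direction of effect for one clinician-assessed secondary endpoint and its diary counterpart, in both efficacy populations.

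The sign reversal follows from the text alone and rests on no assumption. The sizes shown (9.3, 14.7 and 20.0 points) depend on the assumed Merlin rates and on using about 25% for placebo. Significance decisions for this endpoint and all results for the primary endpoint are unaffected.

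**What to change.** In SAP 6.1.4, define prevention of progression as yes for a subject whose lesion reaches Stage 7 without any assessment at Stage 3, 4 or 5, and as no for a subject with any assessment at those stages. State that the same coding applies to the clinician-assessed and subject-assessed versions. This restores the direction of Protocol 10.7.4 and uses the definition of an aborted lesion in Protocol 7.3.1. The smallest change that removes the reversal is to exchange yes and no in the existing sentence.

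While the text is open, the sponsor should also state how to count subjects with no Stage 3–5 assessment who never reach Stage 7, because SAP 7.13.5 allows no imputation for this endpoint.

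The correction costs one sentence and needs no change to data collection, sample size or tests. It should be made before unblinding: under SAP Section 9 it would then be a described SAP amendment, whereas a later correction would have to be reported as a change made after unblinding.

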## 10.7 Efficacy Analysis

The efficacy analysis will be performed on both the MITT and the efficacy evaluable populations. For all duration endpoints the following matrix will be used for analyses:

Population	Analysis	Description	Methods
MITT	Main Analysis	Impute duration for subjects who drop out prior to healing with a duration of 336 hours (14 days x 24 hours).	Hodges-Lehmann estimation methods; Wilcoxon rank sum test to compare arms
	Sensitivity Analysis	Subjects who drop out prior to healing will be considered censored.	Kaplan-Meier estimation methods; Log-rank test to compare arms
EE	Main Analysis	No imputation required since these are complete cases.	Hodges-Lehmann estimation methods; Wilcoxon rank sum test to compare arms

For all endpoints on the occurrence of prevention of progression, counts and percentages will be summarized, and chi-square tests, or Fisher's exact test will be used to compare arms, as appropriate. Fisher's exact tests will be used if any of the expected cell counts in the Rx C crosstabulations are less than 5.

For size endpoints, means, medians, standard deviations and ranges will be summarized. T-tests will be used to compare arms if the sizes are approximately normally distributed, or Wilcoxon rank sum tests will be used if the sizes are markedly non-normally distributed.

For the severity endpoints, counts and percentages will be summarized, and Cochran-Mantel-Haenszel tests will be used to compare the arms.

In order to assess whether there are differences among centers in treatment effects, a Cox proportional hazards model analysis of the duration of herpetic episode will also be performed for the primary duration endpoint and for both the MITT and EE populations. The model will include terms for treatment, center, and treatment by center interaction. A test will be performed to test for the significance of the interaction. This test will be conducted at the 0.10 level of significance. If the interaction is found to be significant, estimates of treatment effect will be provided by center, as well as overall.

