### 7.1.2 Modified Intent-to-Treat (MITT) Population

All subjects who have been entered into the Treatment Phase of the study will be included in the modified intent-to-treat (MITT) Population. It is considered a “modified” intent to treat population in that it does not include all randomized subjects but includes only those randomized subjects who access their treatment, i.e., are told to open their kit. A subject will be included in a treatment group for analysis based upon the treatment to which he or she has been assigned; imputation on the primary endpoint only is planned for the MITT Population – see section 7.13. The MITT Population will be used as the primary analysis population and for all efficacy analyses.

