### **7.13.1 Duration**

Imputation will only be used for analyses of duration endpoints and only in the MITT Population. Duration for subjects who drop out prior to healing will be imputed with a duration of 336 hours (14 days x 24 hours) for the main analyses of duration endpoints in the MITT Population. Hodges-Lehmann technique will be used for estimation and Wilcoxon rank sum tests will be used to compare the groups on duration endpoints in the MITT Population. In addition, subjects who drop out prior to healing will be considered censored in a sensitivity analysis of duration endpoints in the MITT Population and Kaplan-Meier estimation methods will be used with log-rank tests for comparison of the groups.

For analysis of duration in the EE Population, no imputation is required since these are complete cases. Hodges-Lehmann technique will be used for estimation and Wilcoxon rank sum tests will be used to compare the groups on duration endpoints in the EE Population.

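### The 336 h dropout rule reaches pain and hard-scab durations, where it conflicts with the SAP's other rules, and pain unresolved at Day 14 has no value in the main analysis

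*SAP*

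**What the plan says.** **General rule.** Protocol 10.7 introduces its table with "For all duration endpoints the following matrix will be used for analyses". SAP 7.13.1 states "Duration for subjects who drop out prior to healing will be imputed with a duration of 336 hours" for the MITT main analysis, and the matrix in SAP 7.13.5 repeats it. The main method is the Wilcoxon rank sum test with a Hodges-Lehmann estimate. Kaplan-Meier and log-rank, with dropouts censored, form the sensitivity analysis. Protocol 10.1 places hard-scab and pain durations under the same analysis as the classical lesion.

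**Endpoint definitions (SAP 6.1.4).** Pain runs from the first score of mild or worse to two consecutive scores of none, or to complete healing if earlier. Subjects who never have pain "will be assigned a duration of pain value of 0 hours". Those who do not reach no pain within 14 days "will be considered censored immediately following their last pain assessment". Protocol 10.7.7 has the same rules. For hard scab, "This duration will represent the onset of stage 5 until the time of classical lesion healing at stage 6 or 7", whichever comes first.

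**Scope of imputation.** It is stated three ways:
- SAP 7.13.1: "Imputation will only be used for analyses of duration endpoints and only in the MITT Population".
- SAP 7.1.2: "imputation on the primary endpoint only is planned for the MITT Population".
- SAP 8: only missing duration data that queries cannot recover, with the value printed as 336 days.

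**The concern.** The trigger for 336 h is leaving before the lesion heals. It is not failure to observe the end of the endpoint being analysed. For durations that run from first treatment to lesion healing the two coincide. For pain they do not, because pain can stop, or never occur, while the lesion is still present.

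A programmer following SAP 7.13.1 to the letter would move known short or zero pain durations to the worst rank, so the pain result would partly reflect who left the study early. A programmer following SAP 6.1.4, SAP 8 or SAP 7.1.2 would produce a different dataset. Separately, a subject followed to Day 14 and still in pain is not a dropout, so no main-analysis rule supplies a value.

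**Working it through.** **1. The plan's figure.** 14 days x 24 h = 336 h, which reproduces and is the follow-up length from first treatment. The 336 days in SAP 8 would be 336 x 24 = 8,064 h, so it is a unit slip.

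**2. Time origins.** Hard scab starts at Stage 5. Pain starts at first pain, and Protocol 7.2.5.1 has the clinic ask for its onset time at the entry call, so onset may precede treatment. Thus 336 h is not the natural limit of either endpoint.

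**3. The rules side by side, for pain in the MITT main analysis.**

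| Subject | SAP 7.13.1, literal | SAP 6.1.4 | SAP 8 | SAP 7.1.2 |
|---|---|---|---|---|
| Never in pain, leaves before healing | 336 h | 0 h | nothing missing: 0 h | not imputed: 0 h |
| Pain ended, then leaves before healing | 336 h | observed value | observed value | observed value |
| Still in pain on leaving | 336 h | censored | imputed (336 days as printed) | not imputed |
| Followed to Day 14, still in pain | not a dropout: no value | censored | unclear | not imputed |

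The last subject can also be in the EE population, which requires follow-up to healing or 14 days (SAP 7.1.3). For EE, SAP 7.13.1 says no imputation is needed because cases are complete. Neither population's main analysis therefore has a value for this subject. The sensitivity analysis as worded in SAP 7.13.1 names only dropouts as censored.

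**4. What literal overwriting would do.** The documents give no dropout rate, pain duration or scab duration, so every input here is an assumption except the 75 per arm and the two-sided 0.05 level. There were 2,000 runs per scenario.
- Pain: 75 per arm, lognormal with median 60 h and log-SD 0.6, 25% at 0 h.
- Scab: 56 per arm (75 x 0.75 = 56.25, from the 25% aborted rate in SAP 3), lognormal with median 96 h and log-SD 0.4.
- True effect, where present: durations multiplied by 0.75 in the active arm.
- Dropouts: a random fraction whose endpoint had already been observed, overwritten with 336 h.

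| Dropout, active / placebo | Pain: rejection rate, observed kept → overwritten | Scab: observed kept → overwritten |
|---|---|---|
| 5% / 5%, true effect | 0.363 → 0.298 | 0.954 → 0.904 |
| 10% / 10%, true effect | 0.372 → 0.264 | 0.952 → 0.820 |
| 20% / 20%, true effect | 0.362 → 0.184 | 0.960 → 0.648 |
| 15% / 5%, no effect | 0.054 → 0.190 | 0.057 → 0.156 |
| 20% / 5%, no effect | 0.048 → 0.376 | 0.054 → 0.298 |

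With equal dropout and no effect, overwriting left the rejection rate at 0.046-0.052. In the last two rows the mean Hodges-Lehmann estimate for pain moved from about 0 to 7.4 h and 13.8 h. The scab column applies only if healing in SAP 7.13.1 means Stage 7.

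**The case against.** The strongest reply is that the SAP, read as a whole, does not overwrite anything. SAP 8 confines imputation to missing data, and neither a resolved pain episode nor a defined 0 h is missing. SAP 7.1.2 would leave pain and scab unimputed altogether. An endpoint-specific definition can also be taken to override a general rule, and censoring is usable in the planned Kaplan-Meier analysis.

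Much of this stands. A reader might infer that the plan certainly replaces observed outcomes. The documents do not support that, because it follows only from SAP 7.13.1 read literally and against SAP 8. What remains is that the plan does not say which text governs. SAP 9 declares no change from the protocol, whose rule covers all durations.

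A reader might also infer that 336 h distorts the hard-scab test because it exceeds any scab observable after Stage 5 onset. It does not: for a subject whose scab end is unknown, every value above all the observed ones has the same Wilcoxon rank. SAP 6.1.4 also treats Stage 6 as healing for this endpoint, so a subject who reached Stage 6 need not count as leaving before healing.

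The ratio of 336 h to some short pain episode is no measure of size either. No such duration is documented, and a ratio has no direct meaning in a rank test.

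**Conclusion.** The inconsistency is real and should be resolved before unblinding. Four texts (SAP 6.1.4, 7.1.2, 7.13.1 with 7.13.5, and 8) give different values for the same pain data in dropouts. The main analysis has no value for pain unresolved at Day 14, in MITT or EE.

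The consequence is limited to secondary endpoints (clinician-assessed scab) and other endpoints (pain, subject-assessed scab); the primary endpoint is not part of this point. Under the literal reading the cost is power. If dropout differs by arm, the comparison can also be biased. The simulated sizes rest on assumed distributions and dropout rates, and on every dropout having an endpoint already observed. Dropouts still in pain would rank near the top anyway, so the effect at a given dropout rate would be smaller with a mixture.

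A reader might conclude that log-rank must become the main pain analysis. The documents do not require this: the protocol specifies Wilcoxon/Hodges-Lehmann for all durations, and a worst-rank rule makes that method workable.

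**What to change.** In SAP 7.13.1, 7.13.5 and 8, and in Protocol 10.7:
- Apply the 336 h imputation only when the end of that specific endpoint was not observed.
- Keep observed pain and scab durations, and the 0 h value for subjects who never had pain, whether or not the subject later left.
- In the Wilcoxon main analysis (MITT and EE), give the tied worst rank to pain unresolved at Day 14. In MITT, do the same for pain unresolved at dropout and for scab lost to follow-up during Stage 5. Use 336 h, or a common larger value if any observed duration exceeds it.
- Keep Kaplan-Meier/log-rank as the sensitivity analysis with the same endpoint-specific trigger, and extend its censoring to pain unresolved at Day 14.

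Align SAP 7.1.2 with this scope. Reword the SAP 7.13.1 statement that EE needs no imputation so that it allows for unresolved pain. Correct 336 days to 336 hours in SAP 8.

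The cost is wording in the SAP and a matching clarification of Protocol 10.7, recorded under SAP 9. It needs no new data and no method that is not already planned.
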